7.4 Treatment Compliance

Treatment compliance (number of days when the subject actually received the IMP/number of days for which the IMP was prescribed) will be grouped into < 70%, $\ge 70\%$ to < 80%, $\ge 80\%$ to < 90%, and $\ge 90\%$, and its frequency distribution will be

determined overall, for each treatment group, and for the overall brexpiprazole group in the FAS.

7.5 Prior and Concomitant Medications

Numbers and proportions of subjects who used medications (antipsychotics, antidementia drugs, other) before, during, and after the treatment period will be determined by drug class and preferred term of the World Health Organization Drug Dictionary (WHODD) version Global B3 March 2018 overall, for each treatment group, and for the overall brexpiprazole group in the safety analysis set.

7.6 Protocol Deviations

In randomized subjects, numbers and proportions of subjects with major deviations from the protocol will be determined for each deviation category (treatment-related deviations, eligibility-related deviations, failure to discontinue the trial when the subject meets the withdrawal criteria, procedure-related deviations that affect evaluation of the primary endpoint, use of prohibited medications, and overall) and each trial site, overall, for each treatment group, and for the overall brexpiprazole group.

8 Efficacy Analysis

Efficacy analyses will be performed on the FAS. Baseline is defined as the last data obtained prior to initiation of IMP treatment.

8.1 Primary Efficacy Endpoint

8.1.1 Primary Efficacy Analysis

The primary analysis will be performed by MMRM using the OC dataset in the FAS. The model will include treatment group (brexpiprazole 1 mg group, brexpiprazole 2 mg group, or placebo group), time point (Week 2, 4, 6, 8, or 10), medical care category (inpatient or outpatient), prior use of antipsychotics (yes or no), and interaction between treatment group and time point as factors and baseline and interaction between baseline and time point as covariates. Unstructured error variance-covariance structure will be assumed. For a degree-of-freedom approximation, the Kenward-Roger method will be used.

Between-group comparison will be performed by calculating the difference of the least squares mean between each of the brexpiprazole groups and the placebo group at Week 10. The fixed sequence procedure will be used to adjust the multiplicity of testing due to the performance of two comparisons (ie, the brexpiprazole 1 mg group versus the placebo group and the brexpiprazole 2 mg group versus the placebo group) to control the

overall type I error rate. Initially, the brexpiprazole 2 mg group will be compared with the placebo group. Only if the difference is statistically significant at a significance level of 5% (two sided), the brexpiprazole 1 mg group will be compared with the placebo group at a significance level of 5% (two sided).

For each time point, least square means of each treatment group and differences in least square means between each brexpiprazole group and the placebo group, as well as the two-sided 95% confidence intervals (CIs) will be determined.

If any problems in convergence status arise in the estimation of variance components of MMRM, heterogeneous Toeplitz, heterogeneous autoregressive of order 1, and heterogeneous compound symmetry, which are error variance-covariance structures, will be applied in this order, and the first structure that achieves convergence will be used in the primary analysis. If anything other than an unstructured variance-covariance structure is selected, a sandwich estimator for standard errors will be used.

8.1.2 Sensitivity Analyses

8.1.2.1 Sensitivity Analysis for Handling of Missing Data

As a sensitivity analysis for handling of missing data, placebo multiple imputation and tipping point analysis on MNAR assumption will be performed using a pattern-mixture model with multiple imputation.

Multiple imputation analysis will be performed according to the following procedure. The number of imputations will be 100.

- 1) The Fully Conditional Specification (FCS) method will be used to impute missing data. The imputation model for each period will include the medical care category (inpatient or outpatient) and prior use of antipsychotics (yes or no), as well as the CMAI total score for the preceding periods.
- 2) The same MMRM as that of the primary efficacy analysis will be used to analyze the multiple-imputed datasets.
- 3) The MIANALYZE procedure will be used to integrate the analysis results of the multiple-imputed datasets, and the estimate of the difference between each brexpiprazole group and the placebo group at Week 10 and its 95% CI and p-value will be determined.

In placebo multiple imputation, for discontinued subjects in each brexpiprazole group, MNAR will be assumed for missing data and an imputation model based on the placebo group will be used in imputation.

In tipping point analysis, for subjects in each brexpiprazole group who discontinued treatment for any of the following reasons, MNAR will be assumed for missing data after discontinuation.

- Withdrawal for any reason
- Withdrawal due to adverse events (AEs), a lack of efficacy, or consent withdrawal (by subject, legally acceptable representative, or caregiver)
- Withdrawal due to AEs or a lack of efficacy

For subjects in each brexpiprazole group who discontinued treatment for reasons assumed as MNAR, the MAR assumption will be used to impute missing data, add Δ (intergroup differences in MMRM of the primary efficacy analysis) \times k% to the imputed value after withdrawal, and increase k (with 200 as the upper limit) until a statistically significant conclusion is reversed (p > 0.05).

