5.4 Handling of Missing Data

The primary analysis of the primary endpoint will be performed in the observed cases (OC) dataset by mixed models for repeated measures (MMRM) without data imputation for missing data under the "missing at random" (MAR) assumption. As a sensitivity analysis for the handling of missing data, placebo multiple imputation and tipping point analysis will be performed under the "missing not at random" (MNAR) assumption. Details are described in Section 8.1.2.

For analyses of efficacy, safety, and other endpoints, the last observation carried forward (LOCF) method (in which missing post-dose data are imputed by the last observed data after initiation of IMP treatment) will be used as needed.

For pharmacokinetic analysis, no imputation will be performed for missing data.

6 Primary and Secondary Outcome Variables

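### SAP 8.1.2.1 leaves treatment group out of the MAR imputation model; followed as written, the tipping-point analysis starts from a shrunken drug-placebo difference and tips too early

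*SAP*

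**What the plan says.** SAP 8.1.2.1 sets out a three-step multiple imputation by fully conditional specification, with 100 imputations. Step 1 reads: "The imputation model for each period will include the medical care category (inpatient or outpatient) and prior use of antipsychotics (yes or no"). The only further predictors it lists are past scores: "as well as the CMAI total score for the preceding periods". Step 2 reads: "The same MMRM as that of the primary efficacy analysis will be used to analyze the multiple-imputed datasets". That primary model (SAP 8.1.1) contains treatment group and the "interaction between treatment group and time point as factors".

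Two analyses use these steps. For placebo multiple imputation, the SAP says that for discontinued brexpiprazole subjects "an imputation model based on the placebo group will be used in imputation"; this is the only arm-specific wording in the section. For the tipping-point analysis it says that "the MAR assumption will be used to impute missing data", then adds k% of a quantity described as "intergroup differences in MMRM of the primary efficacy analysis", and raises k up to 200 until significance is lost.

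No other section fills the gap. Protocol 6.3 defers to the SAP, SAP 5.4 defers to 8.1.2, SAP 8.1.2.2 calls for MAR multiple imputation without naming a model, and the code in 8.1.3 covers only the primary MMRM.

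**The concern.** An imputation model that omits a factor in the analysis model pulls the imputed values of the arms together. Preceding scores carry part of the treatment effect forward, but not all of it. The between-arm difference in the completed data is then smaller than the one the primary MMRM estimates under its own MAR assumption.

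A tipping-point analysis should show only what happens as one departs from MAR. At k = 0 it should reproduce the primary result. Followed as written, it starts closer to zero while the shift stays scaled to the full primary difference. Part of k is spent before any penalty is applied, so k can no longer be read as the share of the effect removed from dropouts, and a sound result could look fragile. Missing data are expected by design: protocol 3.9.3.2 lists many reasons for mandatory withdrawal, and SAP 3.4 excludes data obtained 7 days or later after the last dose.

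**Working it through.** **Inputs from the documents (SAP section 4).** Difference -5.35, SD 15.06, groups 148 (2 mg), 111 (1 mg) and 148 (placebo), two-sided 5%. As a check on these inputs:

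- 2 mg: SE = 15.06 × √(2/148) = 1.751; noncentral-t power 86.13% (stated 86.1%).
- 1 mg: SE = 15.06 × √(1/111 + 1/148) = 1.891; power 80.47% (stated 80.5%).

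The stated figures reproduce. The documents give no figure for the imputation itself, and no dropout rate, visit correlation or effect time-course. Those three are assumed below.

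**Mechanism by hand.** Let a fraction d of each arm drop out just before Week 10, with correlation ρ between adjacent visits (AR(1)). In a pooled regression the intercept is common to all arms and cancels, so the imputed difference among dropouts is about ρ × (Week 8 difference). The proportional loss is

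s ≈ d × (1 − ρ × Δ8/Δ10).

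With d = 0.20 and ρ = 0.7:

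- full effect already present at Week 8: 0.20 × (1 − 0.7) = 6%
- linear build-up, Δ8/Δ10 = 0.8: 0.20 × (1 − 0.56) = 8.8%

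The simulation of this case gave 6-9%. When all dropout follows Week 2, it gave 16-19%.

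**Large-sample simulation.** 400,000 subjects split 148:111:148, both doses at -5.35, random monotone dropout with equal hazards at Weeks 4 to 10, sequential regression on preceding visits. Baseline and the two factors were left out as balanced. Shrinkage of the 2 mg difference at k = 0, in %, for ρ = 0.5 / 0.7 / 0.85:

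| Structure, onset | 10% dropout | 20% dropout | 30% dropout |
|---|---|---|---|
| AR(1), gradual | 8.4 / 7.4 / 6.3 | 17.0 / 15.0 / 12.9 | 25.6 / 22.6 / 19.5 |
| AR(1), early | 7.6 / 5.7 / 3.6 | 15.3 / 11.5 / 7.4 | 23.1 / 17.4 / 11.1 |
| Compound symmetry, gradual | 7.4 / 7.0 / 6.7 | 15.1 / 13.9 / 13.4 | 22.6 / 21.2 / 20.3 |
| Compound symmetry, early | 4.0 / 2.7 / 2.0 | 8.1 / 5.7 / 4.0 | 12.2 / 8.7 / 6.1 |

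At 20% dropout, -5.35 becomes between -5.35 × 0.83 = -4.4 and -5.35 × 0.96 = -5.1. By-arm imputation returned -5.31 to -5.41 in all 36 settings. A second simulation over 27 settings (early, linear or late onset) gave losses of 4-9%, 8-17% and 10-25% at the three dropout levels. A third over 36 settings gave 3-9%, 6-17% and 9-25%. The difference shrank in every setting of all three.

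**What this does to k.** Shifting all drug-arm dropouts by k% of the difference removes d × k% of it, so a starting loss s uses up k = s/d. At 20% dropout and 15.0% loss, that is 15.0/20 = 75 points. Over the 27 settings the range was 32 to 86 points.

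Take a trial that lands exactly on -5.35 at 20% dropout, using the simulated standard errors of 1.93 (by arm) and 1.90 (pooled):

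- by arm: (5.35 − 1.96 × 1.93) / (0.20 × 5.35) = 1.567/1.07, k ≈ 146
- as written, 15.0% loss: (4.548 − 1.96 × 1.90) / 1.07 = 0.824/1.07, k ≈ 77

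**Tipping point at the planned trial size.** ρ = 0.7, shift applied against the drug to all drug-arm dropouts, median k among trials significant with by-arm imputation:

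| Dropout | Simulation 1, by arm → as written | Simulation 2, by arm → as written |
|---|---|---|
| 20% | gradual 166 → 104; early 173 → 126 | early 190 → 160; linear 190 → 140; late 190 → 125 |
| 30% | gradual 112 → 40; early 116 → 59 | early 130 → 90; linear 130 → 70; late 120 → 60 |

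Simulation 1 used 250 trials per setting and 100 imputations; simulation 2 used 60 trials, 40 imputations and a Week 10 ANCOVA in place of the MMRM. At 10% dropout most trials did not tip by k = 200 under either method. Among trials significant by arm, simulation 1 found the pooled version already non-significant at k = 0 in 3.0-5.8% at 10% dropout, 4.5-13.0% at 20% and 12.4-20.8% at 30%.

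**The case against.** The strongest reply is that silence is not pooling. Step 1 serves two methods, and treatment cannot be a term in a model fitted to placebo subjects only, so a shared list would naturally omit it. SAP 5.4 ties MAR to the primary analysis, done "by mixed models for repeated measures (MMRM) without data imputation for missing data", and that model conditions on treatment. By-arm imputation may well be meant. This stands as a reading of intent, but elsewhere the SAP names treatment group where a model contains it (primary MMRM, robust regression, safety ANCOVAs), and a programmer has no text from which to add it here.

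Second, the shift is written without a sign; adding a negative difference would help the drug. The calculations read it as a penalty, the only reading under which a significant result can be reversed. The sign is a separate point and does not alter the shrunken start.

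Third, the sizes are assumed, and the two tipping simulations differ in level. CMAI is also scheduled at discontinuation, which gives some dropouts a later score and moves them toward the smaller losses. This stands: only the direction is firm.

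Fourth, the error is conservative and confined to sensitivity analyses. This also stands and limits how serious the point is.

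**Conclusion.** The concern holds. As written, step 1 omits treatment group with no by-arm rule for the MAR step, and a program that follows it understates the difference at k = 0 and reaches the tipping point early. The likely size is a loss of 2-9%, 4-17% or 6-26% of the Week 10 difference at 10%, 20% or 30% dropout, given visit correlations of 0.5 to 0.85 and the onset patterns tried. At about 10% dropout the reported conclusion will often not change, because k is capped at 200; at 20-30% the median k falls by roughly 30 to 70 points.

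The two narrower sets of withdrawal reasons were not simulated. The loss there would cost more of k, since all missing values shrink while fewer are shifted. The multiple-imputation version of the 8.1.2.2 normality analyses is affected only if it reuses the step 1 model; its companion without imputation (table CT-5.11.6) is not. Placebo multiple imputation has its own model. The primary MMRM, its power and its type I error are untouched. The plan should be corrected, but the point does not threaten the main conclusion.

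**What to change.** In 8.1.2.1, state that the MAR imputation for the tipping-point analysis is run separately by treatment group, or add treatment group to the imputation model for each period. Either restores the k = 0 estimate; in simulation 2 the two gave similar tipping points. Name the imputation model in 8.1.2.2 and apply the same rule there. Keep the placebo-based model for placebo multiple imputation. Showing the k = 0 estimate beside the primary MMRM result in tables CT-5.11.1 to CT-5.11.3 would make any mismatch visible.

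The cost is one clause in the SAP and one BY or CLASS variable in the program. The standard error rises slightly (1.93 against 1.90 at 20% dropout in simulation 1).

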8.1.2.2 Sensitivity Analysis for Normality Assumption

As a sensitivity analysis for normality assumption, multiple imputation under the MAR assumption will be performed, and the Van Elteren test with medical care category (inpatient or outpatient) and prior use of antipsychotics (yes or no) as strata will be used to compare each brexpiprazole group and the placebo group for each time point, and the Hodges-Lehmann estimator of the intergroup difference will be determined. A robust regression analysis with treatment group, medical care category (inpatient or outpatient), and prior use of antipsychotics (yes or no) as factors and baseline as a covariate will also be performed for each time point. Similar analysis without multiple imputation will also be performed.

8.1.3 Technical Computational Details for Primary Efficacy Analysis

The SAS code for the MIXED procedure to perform the primary efficacy MMRM analysis is shown below.

```
proc mixed;
```

```
class treatment visit subjid hoterm beformed;
```

model change=treatment visit baseline treatment*visit baseline*visit hoterm beformed / ddfm=kr;

repeated visit /type=un subject=subjid;

lsmeans treament*visit / diff cl;

ods output diffs=diffs lsmeans=lsmeans;

run;

*hoterm: medical care category

*beformed: prior use of antipsychotics

8.2 Secondary Efficacy Analyses

- Changes in CMAI subscales (Aggressive Behavior, Physically Non-aggressive Behavior, and Verbally Agitated Behavior) from baseline at Week 10
- Change in CGI-S related to agitation from baseline to Week 10
 The same MMRM analysis as that for the primary endpoint will be performed using the OC dataset.

• CGI-I at Week 10

Each brexpiprazole group will be compared with the placebo group by the Cochran Mantel Haenszel (CMH) Row Mean Scores test with medical care category (inpatient or outpatient) and prior use of antipsychotics (yes or no) as strata using the LOCF dataset. Mean values in each treatment group, differences in mean values between each brexpiprazole group and the placebo group based on CMH Row Mean Scores test, and their two-sided 95% CIs will be calculated. The same analysis will be performed on the OC dataset.

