participation in the trial from the patient (or their legally acceptable representatives) and caregivers. The subject's clinical course will be followed in the same environment (see Section 3.4.2 Inclusion Criteria, 4) such as hospitalization in the same medical facility, institutionalization in the same care facility, and continued care at home from at least 3 weeks before baseline evaluation up to the completion of the examinations scheduled at the completion or discontinuation of IMP administration. After obtaining consent from the patient (or their legally acceptable representatives) and caregiver, the investigator or subinvestigator will perform the specified observations, tests, and investigations to confirm the subject's eligibility before IMP allocation. Subjects who are judged to be eligible in the screening examination and baseline evaluation will be randomized to the brexpiprazole 1 mg, brexpiprazole 2 mg, or placebo group. The IMP allocation will be performed using a dynamic allocation method to minimize bias in background factors (medical care category, prior use of antipsychotics, CMAI total score in baseline assessment) among the treatment groups. Duration of IMP treatment is 10 weeks. The subject will receive brexpiprazole or placebo for 10 weeks according to Section 3.2 Trial Treatments, and undergo periodic observations, tests, and investigations to assess efficacy and safety. The subject will return to the trial site 28 days after the completion of IMP administration for follow-up observation. Discontinued subjects will also undergo follow-up observation.

For subjects who discontinued the trial during the treatment period, the examination at discontinuation will be performed.

The trial period of each subject is from the date of informed consent to the end date of follow-up observation. If subjects have transitioned to the extension trial and commenced IMP administration, follow-up observation will not be performed. In such a case, the trial period is until the end date of evaluation at Week 10 (Day 71).

Protocol 331-102-00088

Figure 3.1-1 Trial Design

Follow-up observation will not be performed for subjects who have transitioned to the extension trial and commenced IMP administration.

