3.7 Measures to Minimize/Avoid Bias

Subjects who meet all the inclusion criteria and do not fall under any of the exclusion criteria will be randomly assigned to the brexpiprazole 1 mg/day group, the brexpiprazole 2 mg/day group, or placebo group at a randomization ratio of 3:4:4. The IMP allocation will be performed using a dynamic allocation method. The details of the randomization method will be described in a separately produced procedural guide for dynamic allocation.

This is a double-blind trial. The IMP allocation manager will prepare a "Table of randomization scheme and codes" (hereinafter randomization table) and conduct IMP coding according to the operating procedures for randomization. The IMP allocation manager will prepare an emergency code list for emergencies, such as when an SAE occurs.

The treatment assignment code will be revealed to neither the subject (including any representatives or caregivers) nor the investigator. The sponsor's staff involved in the

trial (except for those of the Department of Pharmacovigilance [PV department]), including contract research organizations (excluding the bioanalytical laboratory, genetic analysis laboratory, and IDMC), will also remain blind to the treatment assignment codes for the duration of the trial. Prior to the start of the trial, those who are involved in packaging the IMP and the sponsor will confirm that the IMP is not identifiable. The randomization table will be strictly retained until unblinding is performed after finalization of all the case report forms (CRFs) and database.

The emergency code break information will be managed by the IWRS until the completion of the trial. In the event that a subject has a medical emergency and the knowledge of the treatment assignment code is necessary for treatment, the emergency key may be opened for the subject in question (see Section 5.6 Procedure for Breaking the Blind).

The results of CYP2D6 genotyping and plasma drug concentration measurements should not be disclosed until unblinding at the end of the trial. The CYP2D6 genotyping and plasma drug concentration measurements should be performed at the designated laboratories and not at the clinical laboratories of the trial sites.

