3.8.1.3 Randomization

The investigator or subinvestigator will select subjects who meet the inclusion criteria and do not fall under the exclusion criteria on the basis of the results of the screening examination and baseline evaluation. For the clinical laboratory test and 12-lead ECG, the subject's eligibility will be judged on the basis of the results obtained by the central laboratory and central ECG laboratory at the time of screening.

The investigator or subinvestigator will enter information on eligible subjects in the IWRS. Subjects whose registration was confirmed in the IWRS will be randomized to the brexpiprazole 1 mg, brexpiprazole 2 mg, or placebo group using a dynamic randomization method to minimize bias between the treatment groups regarding the following background factors. The date of randomization and randomization number will be recorded in the CRF.

- Medical care category (inpatient or outpatient^a)
- Prior use of antipsychotics^b (yes or no)
- CMAI total score ($\geq 56 \text{ or } < 56$) in the baseline evaluation

^aSubjects who are institutionalized or receiving care at home and visit the trial site as outpatients

^bReceiving antipsychotics in the 6 months prior to the day of baseline evaluation will be considered as "yes."

The investigator or subinvestigator will provide the IMP and subject diary needed for the period up until the next assessment on the basis of the drug number assigned to the subject in the IWRS and give instructions to bring unused IMPs and the completed subject diary to the next assessment.

3.8.1.4 Seven Days After Administration (Week 1, Day 8) to Seventy Days After Administration (Week 10, Day 71)

The investigator or subinvestigator will perform the observations, tests, and assessments shown in Table 3.8-1 and record the results and date of visit.

At visits where blood is collected for measurement of plasma drug concentrations, the date and time of last IMP administration will be recorded.

At visits from 7 days after administration (Week 1, Day 8) until 56 days after administration (Week 8, Day 57), the investigator or subinvestigator will provide the IMP and subject diary needed up until the next assessment on the basis of the drug number assigned to the subject in IWRS and give instructions to bring unused IMPs and the completed subject diary to the next assessment.

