3.8.2.3 Clinical Global Impression–Global Improvement

The rater will assess (by time point evaluation in comparison with the date of baseline evaluation) improvement of agitation associated with dementia of the Alzheimer's type on an 8-point scale using the CGI-I.

3.8.2.4

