6.4.2 Secondary Endpoint Analyses

The secondary endpoint analysis will be performed on the FAS.

- Changes in CMAI subscales (Aggressive Behavior, Physically Non-aggressive Behavior, and Verbally Agitated Behavior) from baseline at Week 10
- Change in CGI-S related to agitation from baseline to Week 10

The same MMRM analysis as that for the primary endpoint will be performed using the OC dataset.

• CGI-I at Week 10

Each brexpiprazole group will be compared with the placebo group by the Cochran Mantel Haenszel (CMH) Row Mean Scores test with medical care category (inpatient or outpatient) and prior use of antipsychotics (yes or no) as strata using the LOCF dataset. Mean values in each treatment group, differences in mean values between each brexpiprazole group and the placebo group, and their two-sided 95% CIs will be calculated.

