placebo group. The IMP allocation will be performed using a dynamic allocation method to minimize bias in background factors (medical care category, prior use of antipsychotics, Cohen-Mansfield Agitation Inventory (CMAI) total score in baseline assessment) among the treatment groups. Duration of IMP treatment is 10 weeks. The subject will receive brexpiprazole or placebo for 10 weeks according to Section 3.2 Trial Treatment, and undergo periodic observations, tests, and investigations to assess efficacy and safety. The subject will return to the trial site 28 days after the completion of IMP administration for follow-up observation. Discontinued subjects will also undergo follow-up observation.

For subjects who discontinued the trial during the treatment period, the examination at discontinuation will be performed.

The trial period of each subject is from the date of informed consent to the end date of follow-up observation. If subjects have transitioned to the extension trial and commenced IMP administration, follow-up observation will not be performed. In such a case, the trial period is until the end date of evaluation at Week 10 (Day 71).

[figure not shown]

Figure 3.1-1 Trial Design

Follow-up observation will not be performed for subjects who have transitioned to the extension trial and commenced IMP administration.

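### The CGI-I test stratifies on two of the three allocation factors; if the omitted one, baseline CMAI category, predicts CGI-I, the test is mildly conservative and its interval slightly wide

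*SAP*

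**What the plan says.** Protocol 3.1 names three factors that dynamic allocation balances: "medical care category, prior use of antipsychotics, CMAI total score in baseline assessment". Protocol 3.8.1.3 repeats them, describing a "dynamic randomization method to minimize bias between the treatment groups regarding the following background factors", and cuts the CMAI total score at 56. SAP 3.1 lists the same third factor: "Cohen-Mansfield Agitation Inventory (CMAI) total score in baseline assessment".

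For CGI-I at Week 10, Protocol 6.4.2 takes medical care category "and prior use of antipsychotics (yes or no) as strata using the LOCF dataset". SAP 8.2 specifies the "Row Mean Scores test with medical care category (inpatient or outpatient) and prior use of antipsychotics (yes or no) as strata", adds an observed-case repeat, and calculates the differences in means "based on CMH Row Mean Scores test, and their two-sided 95% CIs will be calculated". Neither document mentions the CMAI category here, and SAP section 15 lists no change on this point.

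The other secondary endpoints (CMAI subscales and CGI-S) use the primary MMRM, which has a baseline covariate (SAP 8.1.1 and 8.2).

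**The concern.** When arms are balanced on a prognostic factor, the treatment difference varies less from trial to trial than it would under simple randomisation. A test that ignores the factor does not see this: its variance estimate still contains the part the factor explains. The test then rejects too rarely under the null, the interval is wider than it needs to be, and some power is forgone.

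CGI-I is the secondary endpoint exposed to this. It is rated "by time point evaluation in comparison with the date of baseline evaluation", so it has no baseline value of its own and any severity term must come from another variable. The allocation category is the natural candidate.

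The stakes are limited. The fixed sequence covers only the two primary comparisons, so no multiplicity-controlled decision depends on CGI-I.

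**Working it through.** **Plan's own figures.** The documents give no power for CGI-I. The primary calculation (difference 5.35, SD 15.06, groups of 148, 111 and 148, two-sided 5%) is reproduced with the noncentral t:

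- 2 mg v placebo: 5.35 / (15.06 × √(1/148 + 1/148)) = 3.06, power 86.1% (stated 86.1%).
- 1 mg v placebo: 5.35 / (15.06 × √(1/148 + 1/111)) = 2.83, power 80.5% (stated 80.5%).

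The standardised effect, 5.35 / 15.06 = 0.355 SD, is borrowed below as an illustrative CGI-I effect in both dose arms.

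**Approximation.** Let R² be the share of CGI-I variance explained by the CMAI category. If allocation balances that category, the planned standard error is too large by 1/√(1 − R²), and the actual type I error is 2 × [1 − Φ(1.96/√(1 − R²))]:

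| R² | SE inflation | Actual alpha |
|---|---|---|
| 1% | 1.005 | 4.9% |
| 5% | 1.026 | 4.4% |
| 10% | 1.054 | 3.9% |

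**Simulation.** There were 407 subjects, allocated 4:3:4 by minimisation on the three factors.

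- *Allocation (assumed):* the best-balancing arm is taken with probability 0.8, otherwise the arm is random by ratio. The real algorithm is "described in a separately produced procedural guide for dynamic allocation" (Protocol 3.7).
- *Factors (assumed):* 40% inpatient, 30% prior antipsychotics, 50% at 56 or more, independent. Care category and prior antipsychotics explain 2% of variance each.
- *Outcome (assumed):* a latent normal variable cut into seven CGI-I categories, scored 1 to 7, with R² on the latent scale.
- *Interval (assumed):* half-width taken from the CMH standard error.

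Results for the planned four strata against eight strata, LOCF, 80,000 replicates (Monte Carlo SE of the power difference 0.03 to 0.06 points):

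| R² | SE ratio, four/eight | Power change with eight strata, 2 mg | Same, 1 mg | Alpha, four v eight (2 mg) |
|---|---|---|---|---|
| 0 | 0.995 | −0.35 (84.8 to 84.5%) | −0.52 | 5.0 v 5.0% |
| 1% | 1.000 | −0.14 | −0.20 | not listed |
| 2% | 1.005 | +0.15 | +0.04 | 4.8 v 5.0% |
| 3% | 1.010 | +0.36 | +0.38 | not listed |
| 5% | 1.020 | +0.83 (85.4 to 86.3%) | +0.98 | 4.5 v 5.2% |
| 10% | 1.047 | +1.8 (86.3 to 88.1%) | +2.3 | 4.0 v 5.1% |

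The simulated ratios are slightly below the approximation because eight strata cost about 0.5% in standard error: 1.026 × 0.995 = 1.021, against 1.020 simulated at R² 5%. The planned test's own power does not fall as R² rises; the loss is relative to what the third stratum would give.

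**Break-even.** The gain starts at R² of about 1.5 to 2%. With half the subjects at 56 or more, the gap between the two categories is √(R²/0.25) SD:

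- R² 1.5%: √0.06 = 0.24 SD
- R² 2%: √0.08 = 0.28 SD
- R² 5%: √0.20 = 0.45 SD

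**Robustness.**

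- Assignment probability 0.6 or 1.0: gain at R² 5% of 0.8 to 1.0 points (2 mg) and 1.0 to 1.1 (1 mg).
- Observed cases, 15% missing completely at random (assumed), 20,000 replicates: at R² 0, 2, 5 and 10%, changes of −0.6, +0.2, +1.0 and +2.3 points (2 mg) and −0.6, −0.1, +1.1 and +2.7 (1 mg).
- A second simulation with 60% at 56 or more (4,000 runs): planned-test alpha 4.6% and 3.9%, and 2 mg power gains of 0.8 and 1.4 points, at R² 5% and 10%.
- Simple randomisation (8,000 runs): planned-test alpha 4.8 to 5.0% at every R², so the conservatism comes from balancing on a factor that the test then ignores.

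**The case against.** The strongest objection is that the sign of the benefit is unknown. R² is not in the documents, and because CGI-I is itself rated against baseline, it may be low. At R² of 1% the factor is prognostic, yet eight strata give the same interval and slightly less power. This stands, and it is why the point is an option and not a required correction. Against it, the largest modelled loss is about 0.6 points of power, while R² of 5 to 10% gives gains of 0.8 to 2.7 points.

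A second objection is selectivity: the Van Elteren test in SAP 8.1.2.2 uses the same two strata. The same argument applies there in principle. However, that test is a sensitivity analysis for a primary model that already adjusts for baseline, and it sits beside a robust regression with a baseline covariate. The CGI-I analysis has no such companion.

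Third, SAP 8.2 does not write out the interval formula, and the allocation rule, factor prevalences and category cuts are all assumed. The percentages are therefore indicative. The direction does not depend on them, and two simulations with different prevalences agree closely.

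Fourth, eight strata may be sparse. With 15% inpatient, 20% prior antipsychotics and 75% at 56 or more, the smallest stratum in the 2 mg comparison expects 0.15 × 0.20 × 0.25 × 296 = 2.2 subjects. In simulation about one subject per comparison dropped out, and alpha stayed at 4.8 to 5.2%.

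**Conclusion.** The concern holds as a minor efficiency point. One of three allocation factors is missing from the CGI-I test and its interval, in both documents, without a reason. If baseline CMAI category explains 5 to 10% of CGI-I variance, the planned interval is about 2 to 5% wider than with eight strata, the planned test's type I error is about 4.0 to 4.5%, and about 0.8 to 2.3 points of power are forgone (LOCF). Below about 1.5 to 2% there is nothing to gain.

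These sizes rest on an unknown R², an assumed minimisation rule and an effect borrowed from the CMAI total score. The error is on the conservative side, and the trial's main conclusion does not depend on it.

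**What to change.** In SAP 8.2, add the allocation category (baseline CMAI total score 56 or more, below 56) as a third stratum in the CGI-I CMH analysis, for both LOCF and observed cases. Use the 56-point cut, not the median split that SAP 8.3 uses for subgroups, because allocation used 56. State that a stratum containing only one of the two compared arms contributes nothing to the test or the interval, and report how many subjects this excludes. Record the departure from Protocol 6.4.2 in SAP section 15. If the sponsor prefers two strata factors, one sentence giving the reason would do.

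The cost is one variable already held in the IWRS, one phrase in 8.2 and one entry in section 15. If the factor is not prognostic, the statistical price is about 0.35 points of power (2 mg) to 0.5 points (1 mg) with LOCF and about 0.6 with observed cases. Some strata may be small.
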